6.4 Supply and Accountability

CONRAD will oversee the manufacture and analysis/release (Patheon Pharma Services (part of Thermo Fisher Scientific), Whitby, ON, Canada) of the study product under current Good Manufacturing Practices (cGMP).

6.4.1 Study Product Supply

The site will manage the distribution of the study product according to Section 6 of the protocol. The site will be provided with sufficient study product for its designated number of participants. Supplies will be distributed by CONRAD or CONRAD designee.

6.4.2 Study Product Dispensing

TAF/EVG Inserts will be dispensed to clinic staff on behalf of the participant or directly to the participant, upon receipt of a written prescription from an authorized prescriber. An authorized prescriber includes the IoR or a licensed clinician(s) directly responsible to the IoR as noted on the Form FDA 1572 and the Delegation of Authorities (DoA) Log.

6.4.3 Study Product Accountability

Each CRS Pharmacist of Record (PoR) is required to maintain a complete record of all TAF/EVG inserts received and subsequently dispensed. All unused TAF/EVG inserts must be returned to the IND Sponsor, CONRAD, after the study is completed or terminated unless otherwise instructed by the IND Sponsor.

6.4.4 Retrieval of Unused Study Products

All undispensed study product remaining at the end of the study will be recorded by the site and reconciled by the study monitor(s). After reconciliation, the sponsor will provide instruction regarding disposal, storage, or return of product.

6.5 Concomitant Medications

All concomitant medications used within 7 days of Screening will be recorded on CRFs for participants starting at Screening. Participants may use acetaminophen (paracetamol) on an as-needed basis during the study. Concomitant medications include all prescription medications, over-the-counter preparations, vitamins, nutritional supplements, recreational drugs, and herbal preparations.

6.6 Prohibited Medications, Products and Practices

6.6.1 Prohibited Medications and Products

Participants should not use the prohibited medications and products as listed in Appendix IV during the study unless instructed by a clinician in which case they should inform study staff.

6.6.2 Prohibited Practices

[figure not shown]
Female participants will be asked to abstain from receptive oral, anal, or vaginal intercourse and other vaginal practices (e.g., masturbation, douching, tampon use, application of lubricants/spermicides or other related practices) 48 hours prior to and after dosing, except for vaginal intercourse when required by protocol, and for at least 10 days after biopsy.

Male participants will be asked to abstain from insertive oral, anal or vaginal intercourse (including with fingers and toys) 48 hours prior to and after dosing, except for vaginal intercourse when required by protocol, and for at least 10 days after the female participant has a biopsy.

7 STUDY PROCEDURES

An overview of the study visits and evaluations schedule is provided in Appendix I and Appendix II. Presented in this section is additional information on visit-specific study procedures. Visit procedures may be conducted by phone or (with participant consent) off-site if deemed appropriate by the IoR/designee. Any study procedures, including laboratory tests, can be repeated as clinically indicated. Detailed instructions to guide and standardize procedures across sites as well as to specify the visit windows are provided in the MATRIX-004 Study Specific Procedures (SSP) Manual.

Figure 3: Study Visit Schedule

7.1 Pre-screening

As part of participant outreach and recruitment strategies, study staff may pre-screen potential study participants in person or over the phone. During these interactions, study staff may explain the study to potential participants and ascertain elements of presumptive eligibility, to be confirmed at an on-site screening visit. Potential participants invited for screening visits may be advised to bring identity documentation and the required locator information. Additionally, they

will be asked to bring documentation of a normal Pap test within 3 years prior to enrollment if available. Process information (e.g., number of potential participants contacted, number presumptively eligible) may be recorded and stored at the study site in the absence of written informed consent from potential participants (waivers of consent and HIPAA authorization are for pre-screening purposes only). Procedures and documentation will comply with local IRB/IEC requirements. Sites will be responsible for defining pre-screening procedures in their SOPs prior to initiation.

7.2 Screening Visit – Visit 1

Female and male participants will each provide separate written informed consent for screening and enrollment prior to any data collection procedures. Eligibility determination (for female and male participants) will be assessed at Visit 1 and (for female participants) be confirmed at Visit 2. Self-reported elements of eligibility for male participants may be confirmed by phone prior to or during Visit 2, if needed. For female participants, the Screening Visit will include baseline medical history, physical and pelvic examinations, urine pregnancy test (UPT), HIV/STI screening, blood baseline safety tests, and behavioral assessments. For male participants, it will include baseline medical history, directed physical examination (including genital inspection), HIV/STI screening, blood baseline safety tests, and behavioral assessments. Menstruating participants will be scheduled after menstrual flow ceases. Note that if a participant(s) is not able to complete or needs to repeat any of the study procedures conducted at this visit (e.g., blood draw), they may return prior to Visit 2. Labs may be repeated during the screening window per IoR/designee discretion.

Note: Couples will ideally complete their Screening Visit together. However, if needed and at the discretion of the site IoR/designee, the Screening Visit may be conducted on separate days for the female and male participant to accommodate the participants' schedules.

Note: Couples who fail their first screening attempt may be re-screened once at the discretion of the site IoR/designee.

Table 1: Screening Visit – Visit 1 – Female Participants

Screening Visit – Visit 1 – Female Participants	
Component	Procedures
Administrative and Regulatory	
 ● Informed consent process ● Assess eligibility ● Assign a unique Participant Identification (PTID) number ● Collect locator information ● Provide reimbursement ● Schedule next visit/contact, if indicated
Behavioral/Counseling	
 ● Protocol requirements counseling per Section 6.6 and Section 7.10 ● Pre- and post-test HIV counseling, and risk reduction counselling ● Collect demographic information ● Baseline behavioral and acceptability questionnaires

Screening Visit – Visit 1 – Female Participants		
Component	Procedures	
Laboratory	Saliva	
 ○ HIV rapid test(s) (only at sites with CLIA certification)
	Urine	
 ○ Pregnancy test ○ Urine dipstick/urinalysis
	Blood	
 ○ HIV rapid test(s) (not required if conducting saliva testing) ○ HIV RNA test(s) (not required for sites that conduct saliva testing) ○ HBsAg ○ Syphilis ○ Complete blood count (CBC) with platelets ○ Chemistries
	Genital	
 ○ TV, GC, CT testing ○ Pap smear, if indicated ○ Saline/potassium hydroxide (KOH) wet mount for candidiasis and/or bacterial vaginosis (BV), if indicated
Clinical	
 ● Collect medical history ● Collect menstrual history ● Assess concomitant medications (CM) ● Pelvic (with bimanual) exam ● Full physical exam ● Vital signs, weight and height ● Provide available test results 	

Table 2: Screening Visit – Visit 1 – Male Participants

Screening Visit – Visit 1 – Male Participants		
Component	Procedures	
Administrative and Regulatory	
 ● Informed consent process ● Assess eligibility ● Assign a unique Participant Identification (PTID) number ● Collect locator information ● Provide reimbursement ● Schedule next visit/contact, if indicated 	
Behavioral/Counseling	
 ● Protocol requirements counseling per Section 6.6 and Section 7.10 ● Pre- and post-test HIV counseling, and risk reduction counselling ● Collect demographic information ● Baseline behavioral and acceptability questionnaires 	
Clinical	
 ● Collect medical history ● Assess concomitant medications (CM) ● Directed physical exam, including genital inspection ● Vital signs, weight and height ● Provide available test results 	
Laboratory	Saliva	
 ○ HIV rapid test(s) (only at sites with CLIA certification)
	Urine	
 ○ Urine dipstick/urinalysis ○ TV, GC, CT testing
	Blood	
 ○ HIV rapid test(s) (not required if conducting saliva testing) ○ HIV RNA test(s) (not required for sites that conduct saliva testing) ○ HBsAg ○ Syphilis ○ CBC with platelets ○ Chemistries

7.3 Stage 0 Visits – Baseline (no sex)

7.3.1 Enrollment Visit – Visit 2

Female participants only should be scheduled for the Enrollment Visit within 60 days of Screening/Visit 1 and (if applicable) after their menstrual flow ceases. Female participants will return to the clinic where they will have HIV and pregnancy testing and, provided the HIV and pregnancy test results are negative, couples will then be enrolled and randomized 1:1 to vaginally administer the TAF/EVG insert either 1 hour or 4 hours before and after coitus. Female participants will undergo sample collection of blood for PK and CVF for PK, PD and microbiota, self-administer the TAF/EVG vaginal insert in the clinic (should not coincide with menses or vaginal bleeding), complete a behavioral and acceptability questionnaire, and approximately 6 hours after dosing without coitus will undergo sample collection of blood for PK and CVF for PK and PD.

Table 3: Enrollment Visit – Visit 2

Enrollment Visit – Visit 2		
Component		Procedures
Administrative and Regulatory		
 ● Confirm participation ● Confirm eligibility ● Conduct randomization (after eligibility confirmation) ● Review/update locator information ● Provide reimbursement ● Schedule next visit/contact, if indicated
Behavioral/Counseling		
 ● Follow-up 1 (FU1) behavioral and acceptability questionnaire ● Protocol requirements counseling per Section 6.6 and Section 7.10 ● Pre- and post-test HIV counseling, and risk reduction counselling
Clinical		
 ● Review/update medical and menstrual history ● Assess adverse events (AE) post product use ● Assess CM ● Pelvic exam ● Directed physical examination, if indicated ● Vital signs and weight ● Provide available test results
Laboratory	Saliva	
 ○ HIV rapid test(s) (only at sites with CLIA certification)
	Urine	
 ○ Pregnancy test ○ Urine dipstick/urinalysis, if indicated
	Blood	
 ○ HIV rapid test(s) (not required if conducting saliva testing) ○ HIV RNA test(s) (not required for sites that conduct saliva testing) ○ Plasma archive ○ Plasma for PK (pre-dose and 6 hrs post-dose) ○ PBMC for TFV-DP (pre-dose)
	Genital	
 ○ PSA test for semen (pre-dose) ○ Vaginal pH (pre-dose) ○ Vaginal swab(s) for microbiota (pre-dose) ○ Vaginal Gram stain (pre-dose) ○ CVF for PK and PD (pre-dose and 6 hrs post-dose) ○ TV, GC, CT testing, if indicated ○ Saline/KOH wet mount for candidiasis and/or BV, if indicated
Study Product/Supplies		
 ● Self-insertion of 1st dose

7.3.2 Post-dose Biopsy Visit – Visit 3

Female participants only will return to the clinic approximately 24 hours after V2 dosing to undergo sample collection of blood for PK, CVT for PK and immunohistochemistry (IHC), and CVF for PK, PD and microbiota.

Table 4: Post-dose Biopsy Visit – Visit 3

Post-dose Biopsy Visit – Visit 3		
Component		Procedures
Administrative and Regulatory		
 ● Confirm participation ● Review/update locator information ● Provide reimbursement ● Schedule next visit/contact
Behavioral/Counseling		
 ● Protocol requirements counseling per Section 6.6 and Section 7.10
Clinical		
 ● Review/update medical and menstrual history ● Assess AEs and CM ● Pelvic exam ● Directed physical examination, if indicated ● Vital signs and weight ● Provide available test results
Laboratory	Urine	
 ○ Pregnancy test, if indicated ○ Urine dipstick/urinalysis, if indicated
	Blood	
 ○ Plasma for PK ○ PBMC for TFV-DP
	Genital	
 ○ PSA test for semen ○ Vaginal pH ○ Vaginal swab(s) for microbiota ○ Vaginal Gram stain ○ CVF for PK and PD ○ Cervicovaginal biopsies (BXV) for PK ○ BXV for IHC ○ TV, GC, CT testing, if indicated ○ Saline/KOH wet mount for candidiasis and/or BV, if indicated

7.3.3 1-week Post-dose Visit – Visit 4

Female participants only will return to the clinic approximately 7 days after V2 dosing to undergo sample collection of blood for PK and CVF for PK, PD and microbiota.

Table 5: 1-week Post-dose Visit – Visit 4

1-week Post-dose Visit – Visit 4	
Component	Procedures
Administrative and Regulatory	
 ● Confirm participation ● Review/update locator information ● Provide reimbursement ● Schedule next visit/contact
Behavioral/Counseling	
 ● Protocol requirements counseling per Section 6.6 and Section 7.10

1-week Post-dose Visit – Visit 4		
Component		Procedures
Clinical		
 ● Review/update medical and menstrual history ● Assess AEs and CM ● Pelvic exam ● Directed physical examination, if indicated ● Vital signs and weight ● Provide available test results
Laboratory	Urine	
 ○ Pregnancy test, if indicated ○ Urine dipstick/urinalysis, if indicated
	Blood	
 ○ Plasma for PK ○ PBMC for TFV-DP
	Genital	
 ○ PSA test for semen ○ Vaginal pH ○ Vaginal swab(s) for microbiota ○ Vaginal Gram stain ○ CVF for PK and PD ○ TV, GC, CT testing, if indicated ○ Saline/KOH wet mount for candidiasis and/or BV, if indicated

7.4 Stage 1 Visits – Pre sex

7.4.1 Second Dosing Visit – Visit 5

Female and male participants will return to the clinic after a washout period of a minimum of 14 days following V3. Visit 5 should not coincide with menses or vaginal bleeding.

For couples randomized to use the insert 1 hour before and after coitus, female participants will self-administer the TAF/EVG vaginal insert approximately 1 hour prior to coitus and will record both the time of insertion and the time of coitus. The insert may be dispensed at the clinic prior to the scheduled visit and may be self-administered outside the clinic. The couple will return to the clinic and the female participant will undergo sample collection of blood for PK and CVF for PK and PD approximately 6 hours after dosing. Female and male participants will each complete questionnaires after coitus and ideally before sample collection.

For couples randomized to use the insert 4 hours before and after coitus, female participants will self-administer the vaginal insert approximately 4 hours prior to coitus and will record both the time of insertion and the time of coitus. The insert may be dispensed at the clinic prior to the scheduled visit and may be self-administered outside the clinic. The couple will return to the clinic and the female participant will undergo sample collection of blood for PK and CVF for PK and PD approximately 6 hours after dosing. Female and male participants will each complete questionnaires after coitus and ideally before sample collection.

At IoR/designee discretion, the stage may be repeated once if the participant is unable to complete the stage as instructed in the protocol. This may include repeat dosing after a minimum 14-day washout period if the participant administers the insert but does not complete the stage.

Table 6: Second Dosing Visit – Visit 5 – Female Participants

Second Dosing Visit – Visit 5 – Female Participants		
Component	Procedures	
Administrative and Regulatory	
 ● Confirm participation ● Review/update locator information ● Provide reimbursement ● Schedule next visit/contact, if indicated 	
Behavioral/Counseling	
 ● Follow-up 2 (FU2) behavioral and acceptability questionnaires ● Protocol requirements counseling per Section 6.6 and Section 7.10 ● Pre- and post-test HIV counseling, and risk reduction counselling 	
Clinical	
 ● Review/update medical history ● Review/update menstrual history ● Assess AEs and CM ● Pelvic exam ● Directed physical examination, if indicated ● Vital signs and weight ● Provide available test results 	
Laboratory	Saliva	
 ○ HIV rapid test(s) (only at sites with CLIA certification)
	Urine	
 ○ Pregnancy test ○ Urine dipstick/urinalysis, if indicated
	Blood	
 ○ HIV rapid test(s) (not required if conducting saliva testing) ○ Plasma for PK (6hrs post dose)
	Genital	
 ○ PSA test for semen ○ Vaginal pH ○ CVF for PK and PD (6hrs post dose) ○ TV, GC, CT testing, if indicated ○ Saline/KOH wet mount for candidiasis and/or BV, if indicated
Study Product/Supplies		
 ● Self-insertion of 2nd dose (may occur outside clinic)

Table 7: Second Dosing Visit – Visit 5 – Male Participants

Second Dosing Visit – Visit 5 – Male Participants		
Component	Procedures	
Administrative and Regulatory	
 ● Confirm participation ● Review/update locator information ● Provide reimbursement ● Schedule next visit/contact, if indicated 	
Behavioral/Counseling	
 ● Follow-up 2 (FU2) behavioral and acceptability questionnaires ● Protocol requirements counseling per Section 6.6 and Section 7.10 ● Pre- and post-test HIV counseling, and risk reduction counselling 	
Clinical	
 ● Review/update medical history ● Assess AEs and CM ● Directed physical examination, if indicated ● Vital signs and weight ● Provide available test results 	
Laboratory	Saliva	
 ○ HIV rapid test(s) (only at sites with CLIA certification)
	Urine	
 ○ Urine dipstick/urinalysis, if indicated ○ TV, GC, CT testing, if indicated
	Blood	
 ○ HIV rapid test(s) (not required if conducting saliva testing)

7.4.2 Post-dose Biopsy Visit – Visit 6

Female participants only will return to the clinic approximately 24 hours after V5 dosing to undergo sample collection of blood for PK, CVF for PK, PD and microbiota, and CVT for PK and IHC.

Table 8: Post-dose Biopsy Visit

Post-dose Biopsy Visit – Visit 6		
Component		Procedures
Administrative and Regulatory		
 ● Confirm participation ● Review/update locator information ● Provide reimbursement ● Schedule next visit/contact
Behavioral/Counseling		
 ● Protocol requirements counseling per Section 6.6 and Section 7.10
Clinical		
 ● Review/update medical and menstrual history ● Assess AEs and CM ● Pelvic exam ● Directed physical examination, if indicated ● Vital signs and weight ● Provide available test results
Laboratory	Urine	
 ○ Pregnancy test, if indicated ○ Urine dipstick/urinalysis, if indicated
	Blood	
 ○ Plasma for PK ○ PBMC for TFV-DP
	Genital	
 ○ PSA test for semen ○ Vaginal pH ○ Vaginal swab(s) for microbiota ○ Vaginal Gram stain ○ CVF for PK and PD ○ BXV for PK ○ BXV for IHC ○ TV, GC, CT testing, if indicated ○ Saline/KOH wet mount for candidiasis and/or BV, if indicated

7.4.3 1-week Post-dose Visit – Visit 7

Female participants only will return to the clinic approximately 7 days after V5 dosing to undergo sample collection of blood for PK and CVF for PK, PD and microbiota.

Table 9: 1-week Post-dose Visit

1-week Post-dose Visit – Visit 7	
Component	Procedures
Administrative and Regulatory	
 ● Confirm participation ● Review/update locator information ● Provide reimbursement ● Schedule next visit/contact
Behavioral/Counseling	
 ● Protocol requirements counseling per Section 6.6 and Section 7.10

1-week Post-dose Visit – Visit 7		
Component		Procedures
Clinical		
 ● Review/update medical and menstrual history ● Assess AEs and CM ● Pelvic exam ● Directed physical examination, if indicated ● Vital signs and weight ● Provide available test results
Laboratory	Urine	
 ○ Pregnancy test, if indicated ○ Urine dipstick/urinalysis, if indicated
	Blood	
 ○ Plasma for PK ○ PBMC for TFV-DP
	Genital	
 ○ PSA test for semen ○ Vaginal pH ○ Vaginal swab(s) for microbiota ○ Vaginal Gram stain ○ CVF for PK and PD ○ TV, GC, CT testing, if indicated ○ Saline/KOH wet mount for candidiasis and/or BV, if indicated

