6.2 Administration

Each female participant will self-administer the vaginal insert approximately 6 hours prior to sample collection at Visits 2, 5 and 8. The vaginal insert(s) will be placed deep (approximately 4-5 cm) in the vagina.

Participants will self-administer the vaginal insert at the clinic at Visit 2. Participants may self-administer the vaginal insert at the clinic at Visit 5 or outside the clinic prior to Visit 5, i.e., approximately one or four hours before coitus depending on randomization. Participants may self-

administer the vaginal insert at the clinic at Visit 8 or outside the clinic prior to Visit 8, i.e., approximately one or four hours after coitus depending on randomization.

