Behavioral/Counseling	
 ● Follow-up 2 (FU2) behavioral and acceptability questionnaires ● Protocol requirements counseling per Section 6.6 and Section 7.10 ● Pre- and post-test HIV counseling, and risk reduction counselling 	
Clinical	
 ● Review/update medical history ● Review/update menstrual history ● Assess AEs and CM ● Pelvic exam ● Directed physical examination, if indicated ● Vital signs and weight ● Provide available test results 	
Laboratory	Saliva	
 ○ HIV rapid test(s) (only at sites with CLIA certification)
	Urine	
 ○ Pregnancy test ○ Urine dipstick/urinalysis, if indicated
	Blood	
 ○ HIV rapid test(s) (not required if conducting saliva testing) ○ Plasma for PK (6hrs post dose)
	Genital	
 ○ PSA test for semen ○ Vaginal pH ○ CVF for PK and PD (6hrs post dose) ○ TV, GC, CT testing, if indicated ○ Saline/KOH wet mount for candidiasis and/or BV, if indicated
Study Product/Supplies		
 ● Self-insertion of 3rd dose (may occur outside clinic)

Table 11: Third Dosing Visit – Visit 8 – Male Participants

Third Dosing Visit – Visit 8 – Male Participants		
Component	Procedures	
Administrative and Regulatory	
 ● Review/update locator information ● Provide reimbursement ● Schedule next visit/contact, if indicated 	
Behavioral/Counseling	
 ● Follow-up 2 (FU2) behavioral and acceptability questionnaires ● Protocol requirements counseling per Section 6.6 and Section 7.10 ● Pre- and post-test HIV counseling, and risk reduction counselling 	
Clinical	
 ● Review/update medical history ● Assess AEs and CM ● Directed physical examination, if indicated ● Vital signs and weight ● Provide available test results 	
Laboratory	Saliva	
 ○ HIV rapid test(s) (only at sites with CLIA certification)
	Urine	
 ○ Urine dipstick/urinalysis, if indicated ○ TV, GC, CT testing, if indicated
	Blood	
 ○ HIV rapid test(s) (not required if conducting saliva testing) ○ CBC with platelets ○ Chemistries

7.5.2 Post-dose Biopsy Visit – Visit 9

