Female participants only will return to the clinic approximately 24 hours after V8 dosing to undergo sample collection of blood for PK, CVF for PK, PD and microbiota, and CVT for PK and IHC.

Table 12: Post-dose Biopsy Visit

Post-dose Biopsy Visit – Visit 9		
Component		Procedures
Administrative and Regulatory		
 ● Confirm participation ● Review/update locator information ● Provide reimbursement ● Schedule next visit/contact
Behavioral/Counseling		
 ● Protocol requirements counseling per Section 6.6 and Section 7.10
Clinical		
 ● Review/update medical and menstrual history ● Assess AEs and CM ● Pelvic exam ● Directed physical examination, if indicated ● Vital signs and weight ● Provide available test results
Laboratory	Urine	
 ○ Pregnancy test, if indicated ○ Urine dipstick/urinalysis, if indicated
	Blood	
 ○ Plasma for PK ○ PBMC for TFV-DP
	Genital	
 ○ PSA test for semen ○ Vaginal pH ○ Vaginal swab(s) for microbiota ○ Vaginal Gram stain ○ CVF for PK and PD ○ BXV for PK ○ BXV for IHC ○ TV, GC, CT testing, if indicated ○ Saline/KOH wet mount for candidiasis and/or BV, if indicated

7.5.3 Study Exit Visit – Visit 10

Female participants only will return to the clinic approximately 7 days after V8 dosing to undergo sample collection of blood for PK and CVF for PK, PD and microbiota. This visit constitutes the female participants' SEV.

Table 13: Study Exit Visit

Study Exit Visit – Visit 10	
Component	Procedures
Administrative and Regulatory	
 ● Review/update locator information ● Provide reimbursement

Study Exit Visit – Visit 10		
Component	Procedures	
Clinical	
 Review/update medical and menstrual history Assess AEs and CM Pelvic exam Directed physical examination, if indicated Vital signs and weight Provide available test results 	
	
 Pre- and post-test HIV counseling, and risk reduction counselling 	
Laboratory	Saliva	
 HIV rapid test(s) (only at sites with CLIA certification)
	Urine	
 Pregnancy test, if indicated Urine dipstick/urinalysis, if indicated

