7.7 Interim Visits/Contacts

Interim visits may be performed at participant(s) request or as deemed necessary by the investigator at any time during the study, including to conduct point-of-care testing or dispense study product prior to Visits 5 and 8. Male and female participants will be instructed to contact the site at any time during the study if they experience moderate to severe urogenital symptoms (e.g., genital burning, irritation, stinging, pressure, rash, itching, discharge, urgency, dysuria, or hematuria). Female participants will be instructed to contact the site if they experience pelvic/lower abdominal pain or moderate to heavy menstrual bleeding (more than she would have during a normal period). The participant(s) will be asked to come in for an evaluation, as indicated.

Interim visits or procedures (e.g., pregnancy test, physical and/or pelvic examination, blood laboratory assessments, urine dipstick, microscopy, culture, STI testing, wet prep, and/or pH) may be performed as deemed necessary by the investigator. The participant(s) will be asked to come in for an evaluation, as indicated. Interim visits after baseline sampling that require examination or interview due to symptoms will be recorded on CRFs.

When an interim visit occurs in response to an AE experienced by a participant(s), study staff will assess the reported event clinically and provide treatment or refer the participant(s) to appropriate medical care, as necessary. All AEs will be evaluated and follow-up of any observed abnormalities will proceed according to Section 8.3.

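### When dose 2 or 3 is taken outside the clinic, no HIV or pregnancy test is required between the previous dosing visit and the dose; the next required tests come after it

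*Protocol*

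**What the plan says.** **Dose 1.** Section 7.3.1 places the woman's tests ahead of enrollment: "provided the HIV and pregnancy test results are negative, couples will then be enrolled and randomized 1:1". The first insert is then used in the clinic.

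**Doses 2 and 3.** Section 6.2 gives a choice of place: "Participants may self-administer the vaginal insert at the clinic at Visit 5 or outside the clinic prior to Visit 5". It says the same for Visit 8, and Tables 6 and 10 repeat the option. Sections 7.4.1 and 7.5.1 add: "The insert may be dispensed at the clinic prior to the scheduled visit and may be self-administered outside the clinic". The couple then comes to the clinic for sampling about 6 hours after dosing.

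**Tests.** Appendix I requires the woman's pregnancy test at Visits 1, 2, 5 and 8, and her HIV rapid test at Visits 1, 2, 5, 8 and 10. At Visits 3, 4, 6 and 7 pregnancy testing is done only when indicated, and no HIV test is scheduled.

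**Release of product.** Under section 6.4.2 the insert may go "directly to the participant, upon receipt of a written prescription from an authorized prescriber". No test result is named. Section 7.7 allows interim visits for several purposes, "including to conduct point-of-care testing or dispense study product prior to Visits 5 and 8".

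**Positive results.** Sections 9.4 and 9.5 stop product and end participation after a positive HIV or pregnancy test.

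**The concern.** The protocol's position is that a woman who tests positive for pregnancy or HIV should receive no further insert. For an out-of-clinic dose 2 or 3, the required test that would trigger this rule comes after the dose and after an act of condomless coitus that the protocol itself asks for. A site could dispense early, do no interim test, and be fully compliant.

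At stake is avoidable exposure of a woman whose pregnancy or infection was already detectable, and of her partner through the required act. Section 13.7.1 describes the effects of the product on a human fetus as unknown. A positive result at Visit 5 would still prevent dose 3, but it cannot undo dose 2. This is a safety and procedural matter. It does not touch the pharmacokinetic comparisons.

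**Working it through.** The protocol gives no figure of its own here. The check is a trace of the schedule, at nominal times and the minimum washout.

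**Inputs**
- Visit 3 is about 24 hours after dose 1, and Visit 6 about 24 hours after dose 2 (7.3.2, 7.4.2).
- Visit 5 is at least 14 days after Visit 3, and Visit 8 at least 14 days after Visit 6 (7.4.1, 7.5.1).
- Sampling at Visits 5 and 8 is about 6 hours (0.25 day) after dosing (6.2).
- Visits 4 and 7 are at day 7 ± 2 after the dose (7.11).
- Intercourse is barred for 48 hours before and after dosing, except for the protocol act, and for at least 10 days after biopsy (6.6.2).

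**Age of the last required tests at an out-of-clinic dose**
- Dose 2: tests at day 0; Visit 3 at day 1; earliest Visit 5 at 1 + 14 = day 15; dose at 15 − 0.25 = day 14.75. Test age is 14.75 days.
- Dose 3, counting from dose 2: tests at Visit 5, day 0.25; Visit 6 at day 1; earliest Visit 8 at day 15; dose at day 14.75. Test age is 14.75 − 0.25 = 14.5 days.

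These are minimums. The protocol text states no maximum gap, and dosing must also avoid menses.

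**Coitus to the next required tests**, taking the tests at the sampling time
- Stage 1: 6 − 1 = 5 hours (1-hour group); 6 − 4 = 2 hours (4-hour group).
- Stage 2: 6 + 1 = 7 hours; 6 + 4 = 10 hours.

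The 6-hour time is fixed for sampling, not for the HIV and pregnancy tests, so a couple may be tested somewhat earlier. For an outside dose the tests still follow insertion.

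**Permitted intercourse before dose 2**
- Abstinence after biopsy runs to 1 + 10 = day 11.
- Abstinence before dosing starts at 14.75 − 2 = day 12.75.
- The open window is 12.75 − 11 = 1.75 days.

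The same window applies before dose 3, plus the Stage 1 act. Longer schedules widen it.

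**Tests at an early hand-out.** If the insert is handed out at Visit 4 or 7, a test done there falls on day 5 to 9. At the earliest next dose, about day 15, it is 15 − 9 = 6 to 15 − 5 = 10 days old. On the shortest schedule it comes before the window that opens on day 11.

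The share of doses taken outside the clinic without interim testing is not known, so the number of affected doses cannot be given.

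**The case against.** The strongest reply is that nothing here is contradictory. The negative results in section 7.3.1 are a condition of enrollment, not a stated rule for every dose, and sections 9.4 and 9.5 act only once a result is positive. Section 7.7 shows that the team foresaw a contact before Visits 5 and 8, and testing and dispensing can share that contact. A prescriber is involved, menstrual history is reviewed at every visit, and the SSP manual is assigned procedural detail, including dispensing. Couples are low-risk and monogamous, both partners are HIV-negative at entry, contraception has been in place for at least six months, and abstinence covers most of the interval.

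Most of this stands, and it keeps the point small. It does not make a test before the dose mandatory.

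Three stronger readings are tempting but unsupported:
- **A test at release would have prevented every such exposure.** The documents give no detection windows. With intercourse on days 11 to 12.75, a test on day 14.75 comes only 2 to 3.75 days later. It can find only what has become detectable.
- **The whole 14.75 days is time at risk.** The abstinence rule cuts permitted intercourse to about 1.75 days on the shortest schedule.
- **The missing pre-dose label in Tables 6 and 10 shows that the tests come after dosing.** Table 3 does not label its own HIV and pregnancy tests pre-dose either, although the text places them first. For in-clinic dosing the tests could come first; the protocol does not say.

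**Conclusion.** The point holds as a minor safety gap. For an out-of-clinic dose 2 or 3, the protocol requires no HIV or pregnancy test between the previous dosing visit and the dose. The last required tests are at least about 14.5 to 14.75 days old, and the next follow the dose and the required coitus.

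The intervals rest on nominal visit times and the minimum washout. The conclusion is about what the protocol requires; the SSP manual may already set a stricter order. Events should be rare, and a reader should not infer an expected harm or any effect on an analysis. The case for change is that the tests are already scheduled and can be moved to where a positive result can still stop the dose.

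**What to change.** In sections 6.4.2, 7.4.1, 7.5.1 and 7.7, require a negative urine pregnancy test and a negative HIV rapid test from the woman:
- before the insert is released for use outside the clinic, and in Stage 2 before coitus;
- before the dose, when dosing is in the clinic.

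State a short maximum test age, for example within a few days of dosing. A test at Visit 4 or 7 should not satisfy the rule by itself, since it would be about 6 to 10 days old at the earliest dose.

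These tests may replace her Visit 5 and 8 tests. Her HIV rapid test is required again at Visit 10, but the pregnancy entry there reads "Pregnancy test, if indicated". If an end-of-study pregnancy result is wanted, keep the Visit 8 test or require one at Visit 10. The man's tests can stay as scheduled.

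**Cost.** This is a protocol clarification. If the tests are moved, the woman has no more tests than now; an end-of-study pregnancy test adds one per woman, 1 × 32 = about 32 urine tests. The downside is at most one short contact per out-of-clinic dose, so at most two per woman before any repeated stage, of the kind section 7.7 already provides for. A reactive rapid test would delay that stage.
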